1.7 Risk analysis

This study is considered to be a non-significant risk study based on United State Food and Drug administration (FDA) and International Standards Organization (ISO) guidelines due to the daily wear nature of the study. With the potential benefit of this study, the work is considered to be ethically justifiable. Ethical approval will be sought from the University of Manchester Senate Committee on the Ethics of Research on Human Beings (hereafter referred to as Manchester UREC). The work where practical will be conducted in accordance with the ICH Good Clinical Practice Guidelines and the international standard BS EN ISO 14155:2011 'Clinical investigation of medical devices for human subjects'.

Section 2. Resources

2.1 Subject selection

In this work 55 subjects will be recruited and enrolled.

2.1.1 Subject withdrawal and replacement

This study includes three clinical visits. Once the study consent form is signed, the subject is considered to be enrolled on the study. Subjects who have signed the consent form, but who have not completed the first study visit will usually be replaced. All subject data will be included in the final analyses unless there are strong grounds for exclusion; such grounds will be detailed in the final report. At the end the study, all subjects will sign a study exit form.

2.1.2 Subject recruitment

Subjects will be recruited by one or more of following means:

1. Posting study details on The University of Manchester's 'Research Volunteers' website.
2. Correspondence to existing wearers on the Eurolens Research database of subjects.
3. Advertising through a variety of media via a format separately approved by Manchester UREC.

2.1.3 Inclusion criteria

Subjects will only be eligible for the study if:

1. They are between 18 and 40 years of age (inclusive).
2. They understand their rights as a research subject and are willing to sign a Statement of Informed Consent.
3. They are willing and able to follow the protocol.
4. They are an existing silicone hydrogel *reusable* spherical contact lens wearer in both eyes.
5. They have a contact lens spherical prescription between -0.25D and -6.00D (inclusive) based on ocular refraction.
6. They own a wearable pair of spectacles and wear them on the day of the initial visit.
7. At dispensing, they can attain at least 0.20 logMAR distance high contrast visual acuity in each eye with the study lenses within the available power range.
8. They are willing to comply with the wear schedule (at least five days per week and for at least eight hours per day).
9. They agree not to participate in other clinical research for the duration of the study.

2.1.4 Exclusion criteria

Subjects will not be eligible for the study if:

1. They have an ocular disorder, which would normally contra-indicate contact lens wear.
2. They have a systemic disorder, which would normally contra-indicate contact lens wear.
3. They are using any topical medication such as eye drops or ointment, or use any rewetting/lubricating drops whilst on this study.
4. They are aphakic.
5. They have had corneal refractive surgery.
6. They have any corneal distortion resulting from previous hard or rigid lens wear or have keratoconus.
7. They are pregnant or breastfeeding.
8. They have any ocular abnormality which would, in the opinion of the investigator, normally contraindicate contact lens wear
9. They have any infectious disease which would, in the opinion of the investigator, contraindicate contact lens wear or pose a risk to study personnel; or they have any immunosuppressive disease (e.g. HIV), or a history of anaphylaxis or severe allergic reaction.
10. They have taken part in any contact lens or care system clinical research within two weeks prior to starting this study.

2.2 Subject discontinuation

In general, subjects should be discontinued at any time, if it is in their best interests, as judged by the investigator. Reasons for this may include clinical signs of grade 3 or more, lack of motivation, discomfort, repeated refusal to follow instructions or the use of non-study products such as solutions or lenses. Subjects will be discontinued if a serious adverse event occurs or if they miss two or more planned consecutive visits. Subjects who fail to satisfy all the inclusion and exclusion criteria will be discontinued and replaced. Subjects may choose to leave the study at their own request. All discontinuations will be carefully recorded.

2.3 Safety parameters, adverse events and concurrent illnesses

The key safety parameters are the serious and significant adverse events listed in [REDACTED] adverse events are classified as 'serious', 'significant' or 'non-significant').

Clinical assessment is made at the study visit(s) for these parameters. The presence of any ocular adverse event will be reported on CVI report forms and those ocular adverse events described as 'serious' or 'significant' will be detailed in the final report. Similarly,

any concurrent illness that is likely to impact on the relevance and quality of the captured data will be noted on the case report form.

2.3.1 Investigator obligations

At all times the investigator will act in the best interest of the subject. Referral or treatment of an adverse event or other clinical finding should be initiated in the best clinical judgement of the investigator, irrespective of the participation in the clinical study.

2.3.2 Reporting obligations

In the case of a 'serious' or 'significant' ocular adverse event, the Principal Investigator will notify the Industrial Contact Person as soon as possible. Manchester UREC and any regulatory authorities will be informed as required.

2.4 Study termination

If it becomes necessary to terminate the study earlier than planned, the Industrial Contact Person will notify the Principal Investigator who will end the study with the cooperation of other staff members. Manchester UREC will be informed.

2.5 Protocol deviations

Any deviations from this protocol will be recorded, and reported to the Industrial Contact Person as appropriate. Manchester UREC will be informed as necessary.

2.5.1 Protocol amendments

Any amendments will be agreed between the Industrial Contact Person and the Principal Investigator with the cooperation of other staff members. Amendments will be recorded, identified and distributed. Approval from Manchester UREC will be obtained as necessary.

2.6 Study resources

Study products will be stored according to the manufacturer's product instructions.

2.6.1 Lenses

Details of the study lens are provided in Table 2. All lens types are CE marked. Initial lens selection will be as indicated by the manufacturer fitting guidelines.

	Lens A	Lens B
Name	PremiO 1 day	clariti 1day
Manufacturer	Menicon Inc.	CooperVision Inc.
Material	Midafilcon A	Somofilcon A
EWC (%)	56	56
BOZR (mm)	8.4	8.6
Diameter (mm)	14.2	14.1
Spherical powers (D)	-0.25 to -6.00 (0.25 steps)	-0.25 to -6.00 (0.25 steps)

Table 2: Study lenses.**2.6.1.1 Use of lenses**

The study lenses will be worn on a daily wear, daily disposable basis (i.e. removed at end of day and discarded). Lenses should be worn for a minimum of eight hours per day, five days per week. The lenses are also to be worn for a minimum of two hours before attending the follow-up visits.

2.6.2 Care regimen

No care system will be used on this study.

2.6.3 Inventory control

All study lenses will be provided by CooperVision Inc. All worn lenses will be discarded.

**2.6.4 Clinical equipment**

Clinical equipment is regularly maintained and calibrated as required. Standard operating procedures and international standards are used where appropriate.

2.7 Study control

This study is controlled by cross-comparison. Bias will be minimised by randomising the order of assessment. Subjects and investigators will be masked to the two lenses - lenses will be over-labelled. Masking may be 'broken' if deemed necessary, by the Principal Investigator or Industrial Contact Person.

2.8 Documentation

Documents related to this work that require archiving will be kept by Eurolens Research for a period of 10 years after completion of the final report. The Sponsor's permission will be sought before the documents are destroyed.

2.9 Data collection and analysis

Data collected in this work will be recorded on a custom-developed database and an established data trail. Data handling will include export of the study information from the clinical database into spreadsheet format for manipulation, followed by export into a

statistical package for analysis. Most clinical data will be entered directly onto the electronic case report form and is considered to be source data.

2.10 Study completion

The clinical phase of the study will be considered as complete when all subjects have signed the exit statement.

2.11 Confidentiality

All matters related to this work will remain confidential within Eurolens Research, the funding company and any regulatory authority (e.g. Manchester UREC). Eurolens Research will take all reasonable steps to ensure that specific lens-related information is not passed on to study participants unless this is required for clinical management of an adverse event. Personal subject information will not be made available. To cater for this, subjects will only be referred by their unique identity number in the study report. The data activities of Eurolens Research are registered with the data protection officer at The University of Manchester. This study will be performed in accordance with the General Data Protection Regulation (GDPR) and Data Protection Act 2018.

2.12 Study monitoring

In order to provide quality control and quality assurance as part of this work, the study monitor will:

1. Liaise closely with the Principal Investigator.
2. Monitor and ensure the safety of the subjects.
3. Ensure that the investigation is being conducted according to the protocol.
4. Monitor and review (or oversee review of) the study records to ensure accuracy.
5. Document their observations and make them available to relevant authorised parties (e.g. Manchester UREC).
6. Implement the Eurolens Research clinical monitoring standard operating procedure.

2.13 Clinical trial registration

This study will be registered with clinicaltrials.gov in accordance with section 801 of the Food and Drug Administration (FDA) Act which mandates the registration of certain clinical trials of drugs and medical devices.

Section 3. Subject management

3.1 Visit scheduling

Subjects will be required to attend three visits. Acceptable date ranges are shown in Table 3.

Visit	Target	Allowable range
Visit 1: Dispensing 1	N/A	N/A
Visit 2:Follow-up & dispensing 2	7 days from Visit 1	6-10 days from Visit 1
Visit 3: Follow-up	7 days from Visit 2	6-10 days from Visit 2

Table 3: Visits and allowable ranges.

3.1.1 Unscheduled visits

Subjects who attend at their own volition, (or as instructed to do so by the investigator) rather than for a scheduled study visit, will be examined and the visit will be classified as 'unscheduled'. Data collected at these visits will be recorded on the clinical study database.

3.1.2 Missed visits

Subjects not attending for a visit will be contacted and encouraged to return for assessment. If two consecutive study visits are missed, the subject will be discontinued. It is expected that Eurolens Research personnel will attempt all reasonable means of communication in this event, including corresponding with the subject by letter.

3.2 Visit conduct

3.2.1 Pre-enrolment

The subject will receive a study-specific information form outlining the study at least 24 hours before the initial visit.

At a suitable time, each subject will be asked to watch a short on-line information presentation detailing study visits and procedures. They will be asked to complete several multiple-choice questions to gauge their understanding of the study. Upon successful completion of these questions, the subject will be booked to attend the initial visit. Subjects should be asked not to wear their habitual contact lenses on the day of the study visit.

3.2.2 Visit 1

Subjects should attend this visit wearing their spectacles. They will then be required to sign an informed consent form prior to enrolment. A copy of the signed form will be issued to the subject. When the subject has signed the consent form, they are considered to be enrolled on the study.

Subjects will be instructed on the following:

1. Lens handling, application and removal, where necessary.
2. Specific study instructions, such as the importance of not using any other contact lens products.
3. General contact lens information such as the management of red eyes.

The following procedures will be performed (any ocular measurement procedures outlined below will be carried out on each eye):

1. Details of the ocular history and contact lens wearing history of the subject will be noted [REDACTED].
2. Details of general health and medications will be recorded.
3. [REDACTED]
4. [REDACTED]
5. [REDACTED]

6. The investigator will confirm that the subject satisfies all the inclusion and exclusion criteria. Subjects who fail to meet all the criteria at this time will usually be discontinued and replaced. If in the opinion of the investigator, the subject may

be eligible at a later date, the subject may be brought back for up to one repeat visit of this type.

7. The first randomised lens pair [REDACTED] will be fitted and allowed to settle for five minutes. Subjects will apply the study lenses themselves.

8. [REDACTED]

[REDACTED]

[REDACTED]

[REDACTED]

[figure not shown]
[REDACTED]

[REDACTED]

9. [REDACTED]

[REDACTED]

10. The subject will be asked to score the following with reference to appropriate visual analogue scales (0-100) [REDACTED]

11. [REDACTED]

[REDACTED]

12. Lens fit will be assessed using the following evaluations: horizontal and vertical centration, corneal coverage and movement. Normally, for an acceptable fit, centration and movement will fall within currently accepted clinical criteria [between 1 and +1 on a -2 to +2 grading scale [REDACTED] If the lens is graded as 'unacceptable' (i.e. any of the grades are +2 or -2), the investigator should state why.

13. Subjects will be given a supply of over-labelled contact lenses [REDACTED]. The subject will then be discharged and asked to return for a one-week follow-up visit wearing the study lenses which need to have been worn for at least two hours. Subjects should be asked to wear their lenses for a minimum of eight hours per day and to wear their lenses every day until the next visit unless he/she experiences symptoms such as redness, discomfort etc. on any given day.

[REDACTED]

[REDACTED]

[REDACTED]

[figure not shown]
3.2.3 Visit 2 – follow-up 1

Subjects should attend wearing their study lenses which should have been in situ for at least two hours. Subjects who attend without lenses in situ for at least two hours will usually be rescheduled.

1. Any medical or ocular issues since the last visit will be recorded.
2. [REDACTED]
3. [REDACTED]
4. Retrieval of any unused lenses.
5. [REDACTED]
6. The subject will be asked to score the following with reference to appropriate vertical visual analogue scales (0-100) [REDACTED]

▪ Vision

7. [REDACTED]

The subject will then be discharged and asked to return for a one-week follow-up visit wearing the study lenses which need to have been worn for at least two hours. Subjects should be asked to wear their lenses for a minimum of eight hours per day and to wear their lenses every day until the next visit unless he/she experiences symptoms such as redness, discomfort etc. on any given day.

3.2.4 Visit 3 – follow-up 2

Subjects should attend wearing their study lenses which should have been in situ for at least two hours. Subjects who attend without lenses in situ for at least two hours will usually be rescheduled.

Any medical or ocular issues since the last visit will be recorded.

1. [REDACTED]
2. [REDACTED]
3. Retrieval of any unused lenses.
4. [REDACTED]
5. The subject will be asked to score the following with reference to appropriate vertical visual analogue scales (0-100) [REDACTED]

Three thick black horizontal bars stacked vertically, with a small gap between the top two.

- Vision

A horizontal bar chart with seven categories on the y-axis and a single data series on the x-axis. The categories are represented by black bars of varying lengths. The x-axis is labeled with the number '1' at the far right. The bars are ordered from top to bottom as follows: Category 1 (shortest), Category 2 (medium), Category 3 (longest), Category 4 (longest), Category 5 (medium), Category 6 (shortest), and Category 7 (longest).

Category	Value
1	1
2	1
3	2
4	2
5	1
6	1
7	2

6. [REDACTED]

[REDACTED]

At the final visit (or when the subject is discontinued at an earlier visit) the subject will sign a study exit statement acknowledging that the work is complete, although they may have been asked by the investigator to attend a post-study follow-up visit, and that they should continue to use their lenses and solutions as advised, and seek aftercare for their contact lenses. A copy of this signed form will be issued to the subject.

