3.3 Monitoring subject compliance

Subjects are required to adhere to the instructions provided during this clinical investigation. This will be confirmed at the study visits by verbal questioning of the subject by the investigator.

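### Does rescheduling subjects who attend follow-up without lenses in place bias the subjective scores toward well-tolerated days?

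*Combined protocol and SAP*

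**What the plan says.** Section 3.2.2 (step 13), repeated at the end of Section 3.2.3, tells subjects to "wear their lenses every day until the next visit unless he/she experiences symptoms such as redness, discomfort etc. on any given day". The same sentences ask them to return for follow-up with the study lenses already worn for two hours. Section 2.6.1.1 states that requirement separately: "The lenses are also to be worn for a minimum of two hours before attending the follow-up visits". For anyone who does not meet it, Sections 3.2.3 and 3.2.4 say: "Subjects who attend without lenses in situ for at least two hours will usually be rescheduled".

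Table 3 in Section 3.1 gives Visit 2 a target of 7 days and a range of "6-10 days from Visit 1"; Visit 3 has the same range counted from Visit 2. The 0–100 subjective scores are a step within each follow-up visit. Section 1.5 makes lens fit primary, vision secondary and everything else tertiary. Section 1.6 frames the study as non-inferiority of clariti to PremiO and names subjective responses among the data to be compared.

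Several provisions bear on what is known about a moved visit:

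- Section 2.5: "Any deviations from this protocol will be recorded".
- Section 2.3: "The presence of any ocular adverse event will be reported on CVI report forms".
- Section 3.1.1, on unscheduled visits: "Data collected at these visits will be recorded on the clinical study database".
- Section 3.3, on compliance: "This will be confirmed at the study visits by verbal questioning of the subject by the investigator".
- Sections 3.2.3 and 3.2.4 also have medical or ocular issues since the last visit recorded.

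**The concern.** Read together, these rules let the timing of a patient-reported score depend on how well the lens being scored is tolerated. A subject whose eye is sore on the visit day may come without lenses, be sent away, return up to three days past target (10 − 7 = 3) still in window, and score the lens on a better day. The rescheduling sentence does not separate a subject who forgot from one whose eye hurt, and no visible text asks for a score first.

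The moved visit gives a complete record, so the subject counts promised in Section 3.4 would not reveal it. Masking and random order do not help, because the selection follows tolerance rather than knowledge of the brand. If it happened more often with clariti, its observed deficit would shrink and a false claim of non-inferiority on the subjective scores would become more likely.

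**Working it through.** **The plan's own figure.** Section 1.6 gives one-sided alpha 0.05, SD 28.4, a difference of 10 units, 51 completers and power 0.80. Treating 28.4 as the SD of within-subject differences:

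- n = [28.4 × (1.645 + 0.842) / 10]² = 49.9, so 50 by the normal formula.
- By the paired t-test, power at 51 is 0.798, and 52 is the first n to reach 0.80.

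The stated 51 is reproduced to within one subject, so these inputs can be used below.

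**Inputs that must be assumed.** The documents give no rate of symptomatic non-wear and no score for a symptomatic day. The 10 units is called a meaningful difference, not a margin, and both it and the SD belong to a variable whose name is redacted. For illustration, take 10 as the margin, a score 20 to 30 units lower on the symptomatic day, and full recovery by the new date.

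**Formulas.**

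- Bias b = (rate with clariti − rate with PremiO) × drop.
- SE = 28.4/√51 = 3.977; critical t on 50 df = 1.676.
- One-sided error at a true deficit of 10 = P(noncentral t, 50 df, noncentrality b/3.977, exceeds 1.676).

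**Results.**

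| Visits moved, clariti vs PremiO | Net subjects of 51 | Bias (units) | One-sided error |
|---|---|---|---|
| Equal rates | 0 | 0 | 5.0% |
| 2% vs 1% | 0.01 × 51 = 0.5 | 0.2 to 0.3 | 5.5–5.8% |
| 4% vs 1% | 0.03 × 51 = 1.5 | 0.6 to 0.9 | 6.7–7.8% |
| 1% vs 4% | −1.5 | −0.6 to −0.9 | 3.6–3.1% |
| 15% vs 5% | 0.10 × 51 = 5.1 | 2 to 3 | 12.5–18.4% |

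Per net subject, the bias is 20/51 to 30/51 = 0.39 to 0.59 units and the error 6.1–6.7%. If the score recalls the whole week and so keeps half of the drop, this falls to 0.20 to 0.29 units and 5.5–5.8%. An error of 10% needs b = 1.46, that is 51 × 1.46/30 = 2.5 to 51 × 1.46/20 = 3.7 net subjects.

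**What must hold for any bias.**

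1. Symptoms fall on the visit day itself.
2. The subject attends without two hours of wear. The symptom exception qualifies wear on the days up to the next visit; the two-hour requirement for the visit carries no stated exception, so excusal on the visit day is an inference.
3. The visit is rescheduled, which the text says happens usually, not always. That it stays in window is also inferred, since the sentence does not mention Table 3.
4. The lens is tolerated at the new date. Section 2.2 lists discomfort as a possible reason for discontinuation, so some lasting intolerance leaves by that route.
5. The score reflects that day rather than the week. The recall wording is not visible.
6. All this is more frequent with one lens. Nothing in the documents says so, and the same rule applies to both lenses.

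**The case for a change.** The strongest argument for a change is that a score not taken on the bad day cannot be recovered later, while asking for one costs a single case report form item. A flagged score before rescheduling, a count by lens and one sensitivity analysis would show whether the conclusion depends on moved visits. If few visits moved, the burden would be almost nil; if many did, the sponsor would need to know.

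Part of this stands. The visible text does permit the shift, none of the recording provisions visibly requires a score for the symptomatic day, and how often visits were rescheduled with each lens is worth knowing.

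The rest is weaker. Attending without two hours of wear departs from Section 2.6.1.1, so it falls under the deviation records, and ocular issues and compliance are asked about at each visit. A count by lens with reasons can probably be drawn from these without new text. The added score would be given with the lens out, so substituting it mixes symptoms with a different measurement condition, particularly for vision. It could not correct the main analysis, and with perhaps one or two such scores the comparison would say little. Nor can one conclude that no score is taken: many steps and scored items in Sections 3.2.2 to 3.2.4, and the material directly after the wear instruction, are redacted.

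**Conclusion.** No change to the plan is needed. Requiring lenses in place for a set time before assessment is a fair standardisation choice, and its price is a possible selection of better days for the subjective scores. That price is zero if both lenses are affected equally and runs in either direction otherwise. On the assumptions stated, it is about half a unit on a 100-unit scale per net subject moved; an error above 10% would need about three or more net subjects in one direction, and the documents give no ground to expect that. The primary outcome is outside the concern, because lens fit needs a lens in the eye. The exposed outcomes are lower-tier: subjective scores are tertiary, and scored vision is not shown to be the secondary vision outcome. If the deviation and visit records show more rescheduling with one lens, whoever writes the report can give the counts and reasons by lens and read the subjective scores accordingly. This conclusion rests on 28.4 being the SD of paired differences, on 10 units serving as the margin, and on the assumed drop of 20 to 30 units.
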